### Study Design

This study is a long-term, open-label study using rhPTH[1-84] for the treatment of adult male and female subjects with hypoparathyroidism. Subjects can enroll if they either previously completed the rhPTH[1-84] RELAY study (PAR-C10-007) (8 weeks of active therapy) and/or completed the REPLACE study (CL1-11-040) (Visit 18).

The goal of this study is to optimize rhPTH[1-84] dosing while reducing calcitriol and oral calcium (carbonate or citrate) supplementation to as low as safely possible and maintaining total serum calcium levels. Dose adjustments to rhPTH[1-84] and to the calcium/calcitriol supplements and safety monitoring of calcium levels are explained in Appendix 2, rhPTH[1-84] and Supplement Titration Guideline.

- The starting dose of rhPTH[1-84] for this study will be 25 or 50 µg SC once daily (QD).

- Subjects may have their rhPTH[1-84] dose adjusted by the investigator at any time during the study, with the goal of achieving or maintaining total serum calcium levels in the range of 8.0 to 9.0 mg/dL.
- If **ANY** predose (trough) total serum calcium is >11.9 mg/dL study drug will be stopped.
- Subjects will have blood draws to assess total serum calcium levels (which may be performed locally) 3 to 5 days after **ANY** dose adjustment of rhPTH[1-84], after any significant change in doses of calcium and/or calcitriol supplements, or at any other time at the discretion of the investigator.
- Study visits during the first 12 months of the study will be conducted at Weeks 1 (baseline), 4, 8, and then every 8 weeks thereafter up to Week 48 (Visit 8). The Week 52 visit (Visit 9) is scheduled 4 weeks later.
- At any time following the Week 16 (Visit 4), subjects who are on a stable dose of rhPTH[1-84] and have a 24-hour urine calcium >300 mg (males) and >250 mg (females) may be treated for hypercalciuria with calcium-sparing diuretics, if this therapy had not been introduced prior to the study.
- At the end of Week 52, subjects will be invited to extend their study drug regimen until January 2018 or after the completion of the last patient's Month 72 visit, whichever comes last.
- During this time, subjects will return to the clinic for interim visits every 2 months (Months 14, 16, 18, etc).

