#### Calcium and Phosphate Regulation

Serum calcium and phosphate levels are regulated principally by parathyroid hormone (PTH), the active vitamin D metabolite 1,25-dihydroxyvitamin D (1,25[OH]2 vitamin D; calcitriol), and calcitonin. PTH maintains an inverse relationship with serum calcium. Normal total serum calcium levels (generally 8.4 to 10.2 mg/dL) and serum phosphate levels (2.5 to 4.5 mg/dL) are regulated to yield a calcium phosphate product of approximately 35 mg/dL. This product is important because of the potential for calcium phosphate salts to be deposited in soft tissues. Levels of the calcium phosphate product that exceed 50 mg/dL are believed to place patients at risk for ectopic soft tissue calcification. PTH is synthesized and secreted by the parathyroid glands primarily in response to a fall in serum calcium levels. Through concerted actions on the kidney and bone, PTH is the principal regulator of plasma calcium homeostasis. In the kidney,

PTH increases renal tubular reabsorption of calcium (while inversely inhibiting phosphate reabsorption) and increases the synthesis of 1,25(OH)2 vitamin D from its precursor 25-hydroxyvitamin D (25[OH] vitamin D). Although 1,25(OH)2 vitamin D has a short in vivo half-life (approximately 6 hours), it directly increases intestinal calcium and phosphate absorption. In bone, PTH increases the efflux of calcium from bone, both from the rapidly exchangeable pool of calcium within bone, and by increasing the number and activity of osteoblasts and osteoclasts, thereby increasing bone turnover. As PTH also acts to inhibit the reabsorption of phosphate in the proximal nephron, it prevents an increase in plasma phosphate levels that could result from increased intestinal phosphate absorption and efflux of phosphate from bone. Calcitonin, secreted by C-cells of the thyroid gland, decreases serum calcium by inhibiting bone resorption and promoting renal tubular calcium excretion, but its effects are relatively minor in comparison to those of PTH and 1,25(OH)2 vitamin D ([Bilezikian et al. 2001](#)).

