- Adjustment of supplemental calcium and calcitriol regimens will be based on serum calcium levels, with the goal to be a reduction or removal of calcitriol treatment to the maximum degree clinically possible and to decrease the prescribed oral calcium supplementation to  $\leq 500$  mg daily.
- Subjects will have blood draws to assess total serum calcium levels (which may be performed locally) 3 to 5 days after ANY dose adjustment of rhPTH[1-84], after any significant change in doses of calcium and/or and calcitriol supplements, or at any other time

at the discretion of the investigator. Results of local total serum calcium levels will be recorded in the source document.

[figure not shown]
- Once a subject achieves a stable serum calcium (target: between 8.0 and 9.0 mg/dL) with the minimum doses of supplements possible, they will be maintained at that dose of rhPTH[1-84].
- If ANY predose (trough) total serum calcium is > 11.9 mg/dL study drug will be stopped. Once total serum calcium returns to the normal range, rhPTH[1-84] can be reintroduced. The rhPTH[1-84] dose may be maintained at the previous level if reductions in oral calcium supplements and/or calcitriol are possible. If oral calcium supplements have been previously reduced to ≤ 500 mg daily and calcitriol has been eliminated, then rhPTH[1-84] should be reintroduced at the next lowest dose level and supplemental oral calcium and calcitriol should then be adjusted accordingly to obtain a predose total serum calcium level of approximately 8.0 to 9.0 mg/dL.
- If the predose total serum calcium level remains above 10.0 mg/dL for two or more safety assessments or study visits on normal dietary intake and study drug alone, then the rhPTH[1-84] dose may be reduced to the next lowest dose level and supplemental oral calcium and calcitriol then adjusted accordingly to obtain a predose total serum calcium level of approximately 8.0 to 9.0 mg/dL. Study medication will be stopped if the predose total serum calcium remains above the upper limit of the laboratory normal range (ULN) for two or more safety assessments or study visits (no more than 5 days apart) at the lowest dose regimen, following withdrawal of all supplementary oral calcium and calcitriol therapy. Further choices on adaptation of treatment regimens, reinstitution of previous therapy, or discontinuation from study will be made in consultation with the Shire medical monitor.

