## Appendix 2                      RHPATH[1-84] AND SUPPLEMENT TITRATION GUIDELINE

In this study the goal is to continue rhPTH[1-84] dosing and to reduce calcitriol and oral calcium (carbonate or citrate) supplementation to as low as safely possible, while maintaining total serum calcium levels. In patients with hypoparathyroidism treated with oral calcium and calcitriol, it is suggested to maintain total serum calcium levels in the lower half of the normal range (eg, between 8.0 and 9.0 mg/dL; [Shoback 2008](#)). This is to reduce symptoms and to avoid the hypercalciuria which can occur in the hypoparathyroid patient on calcitriol and oral calcium supplementation ([Horwitz and Stewart 2008](#)). In the current trial, all subjects will receive rhPTH[1-84]. Hence, down-titration of calcitriol and oral calcium must be undertaken, where appropriate, to avoid hypercalcemia. At all times, changes in calcitriol and oral calcium dosing should be undertaken at the discretion of the investigator, based on total serum calcium concentrations and the subject's clinical condition.

To help facilitate a more standardized approach to dose adjustment across study centers, the following guideline has been prepared. The guideline is non-mandatory but the approach suggested should be assessed when adjustments in calcitriol and oral calcium are being considered. In the guideline, all references to total serum calcium levels indicate "predose" (trough) values drawn prior to administration of study drug, rhPTH[1-84] (ie, approximately 23 to 24 hours after the previous injection).

The order and magnitude of subsequent reductions in either calcitriol or oral calcium supplementation is left to the investigator's discretion, based on individual subject response. After any change in the rhPTH[1-84] dose, or a significant change in calcitriol or oral calcium supplement dose, a total serum calcium level **MUST** be measured 3 to 5 days later for safety purposes (unless earlier or more frequent testing is clinically required) and to guide further changes in supplement doses.

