### Significant Hypercalcemia

Any instances of significant hypercalcemia, which is defined as any total serum calcium level of > 11.9 mg/dL (even on a non-trough measurement), require **MANDATORY** immediate stopping of rhPTH[1-84] treatment. Suspension of dosing with calcitriol and oral calcium as clinically appropriate and testing of serum total calcium levels at least daily should be undertaken until the subject's serum total calcium returns to the normal range. Other clinically appropriate actions for the treatment of significant hypercalcemia should be undertaken as usual by the investigator to ensure subject safety. Thereafter, rhPTH[1-84] can be reintroduced with clinically appropriate doses of calcitriol and oral calcium, with the aim to avoid further episodes of abnormal serum calcium.

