3.1. General Description

This study is a long-term, open-label study using rhPTH[1-84] for the treatment of adults with hypoparathyroidism. Subjects can enroll if they either previously completed the NPSP558 RELAY study (PAR-C10-007) (8 weeks of active therapy) and/or completed the REPLACE study (CL1-11-040) (Visit 18).

The goal of this study is to optimize rhPTH[1-84] dosing while reducing calcitriol and oral calcium (carbonate or citrate) supplementation to as low as safely possible and maintaining total serum calcium levels. Dose adjustments to rhPTH[1-84] and to the calcium/calcitriol supplements and safety monitoring of calcium levels are explained in protocol Appendix 2, rhPTH[1-84] and Supplement Titration Guideline.

- The starting dose of rhPTH[1-84] for this study will be 25 or 50 µg SC once daily (QD)
- Subjects may have their rhPTH[1-84] dose adjusted by the investigator at any time during the study, with the goal of achieving or maintaining total serum calcium levels in the range of 8.0 to 9.0 mg/dL.
- If **ANY** predose (trough) total serum calcium is >11.9 mg/dL study drug will be stopped.
- Subjects will have blood draws to assess total serum calcium levels (which may be performed locally) 3 to 5 days after **ANY** dose adjustment of rhPTH[1-84], after any significant change in doses of calcium and/or calcitriol supplements, or at any other time at the discretion of the investigator.
- Study visits during the first 12 months of the study will be conducted at Weeks 1 (baseline), 4, 8, and then every 8 weeks thereafter up to Week 48 (Visit 8). The Week 52 visit (Visit 9) is scheduled 4 weeks later.
- At any time following the Week 16 (Visit 4), subjects who are on a stable dose of rhPTH[1-84] and have a 24-hour urine calcium >300 mg (males) and >250 mg (females) may be treated for hypercalciuria with calcium-sparing diuretics, if this therapy had not been introduced prior to the study.
- At the end of Week 52, subjects will be invited to extend their study drug regimen until January 2018 or after the completion of the last patient's Month 72 visit, whichever comes last..
- During this time, subjects will return to the clinic for interim visits every 2 months (Months 14, 16, 18, etc).

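### Appendix 2 leaves out Section 3.1's conditional ULN stop and says 'Maintain' even at a second qualifying reading, and neither text orders the repeat draw that the stop depends on

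*Protocol*

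**What the plan says.** Section 3.1 of the protocol gives three rules on high calcium that bear on the rhPTH[1-84] dose.

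- Any predose value above 11.9 mg/dL stops study drug.
- If predose calcium stays above 10.0 mg/dL at two or more assessments on diet and study drug alone, the dose may be lowered one level. This is permissive.
- "Study medication will be stopped if the predose total serum calcium remains above the upper limit of the laboratory normal range (ULN") at two or more assessments or visits, "no more than 5 days apart) at the lowest dose regimen, following withdrawal of all supplementary oral calcium and calcitriol therapy". This is mandatory once its conditions are met, and further decisions go to the medical monitor.

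The synopsis (Study Design) directs the reader elsewhere: "Dose adjustments to rhPTH[1-84] and to the calcium/calcitriol supplements and safety monitoring of calcium levels are explained in Appendix 2". Its own list gives only one stop: "predose (trough) total serum calcium is >11.9 mg/dL study drug will be stopped". SAP Section 3.1 repeats both statements.

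Appendix 2 carries only the first rule, in a wider form, for significant hypercalcemia, "which is defined as any total serum calcium level of > 11.9 mg/dL (even on a non-trough measurement"). It does not mention ULN. In both post-baseline sets (interim safety check, and Weeks 4 to End of Study) the rhPTH[1-84] column for 9.1-10.5 and 10.6-11.9 mg/dL reads 'Maintain'. On its own status it says: "The guideline is non-mandatory but the approach suggested should be assessed when adjustments in calcitriol and oral calcium are being considered".

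**The concern.** A site that titrates from the Appendix 2 tables would see one stop, at 11.9 mg/dL, and an unqualified 'Maintain' below it. For a subject already at the lowest dose and off supplements, the only action in those rows is to reduce or eliminate supplements, which are already zero. The site could therefore continue dosing a subject whom Section 3.1 says must stop. Nothing in the tables would tell it that a repeat within 5 days decides the matter. The consequence is longer exposure to persistent hypercalcemia in a study whose primary objective is long-term safety and for which the SAP (Section 5.5) identifies no DSMB.

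**Working it through.** The plan has no figure to reproduce. The check compares the texts and then does some simple arithmetic on ranges and visit spacing.

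**Step 1. The two texts side by side.** The subject is at 25 µg with no oral calcium and no calcitriol. That 25 µg is the lowest regimen is inferred from the strengths supplied (25, 50, 75 and 100 µg, Section 5.1.1).

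| Predose calcium | Section 3.1 | Appendix 2 | Conflict? |
|---|---|---|---|
| 9.1 mg/dL up to ULN | No stop | Maintain | No |
| One reading above ULN, not above 11.9 | No stop yet | Maintain | No |
| Second reading above ULN, not above 11.9, within 5 days | Stop | Maintain | **Yes** |
| Second reading above ULN, not above 11.9, more than 5 days later | Not triggered as worded | Maintain | No, but the rule goes untested |
| Above 11.9 | Stop (predose sample) | Stop (any sample) | No; Appendix 2 is wider |

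The rows apply at every check, including the second high one, so the third line is a genuine contradiction.

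**Step 2. Calcium range in which the conflict can occur.** The only ULN figure is general: "Normal total serum calcium levels (generally 8.4 to 10.2 mg/dL").

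- Width = 11.9 − ULN = 11.9 − 10.2 = 1.7 mg/dL. This is the top 10.5 − 10.2 = 0.3 mg/dL of the 9.1-10.5 row plus the whole 10.6-11.9 row.
- Assumed ULN of 10.0: 11.9 − 10.0 = 1.9 mg/dL.
- Assumed ULN of 10.5: 11.9 − 10.5 = 1.4 mg/dL, all in the 10.6-11.9 row.

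**Step 3. Would the schedule supply the second reading?** Take visits held within their windows and no unscheduled draw.

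- Week 1 interim check to Week 4: the check falls at most 5 + 2 = 7 days after baseline, and Week 4 at least 28 − 7 = 21 days after. The gap is at least 21 − 7 = 14 days.
- Later year-1 visits are 4 or 8 weeks apart with ±7-day windows. The gap is at least 28 − 14 = 14 days.
- Extension visits are 2 months apart (at least 56 days) with ±2-week windows. The gap is at least 56 − 28 = 28 days.

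No pair of scheduled assessments above falls within 5 days. Appendix 2 requires a 3 to 5 day check after a change in rhPTH[1-84] or a significant change in supplements. A subject moved down to 25 µg, or off the last supplement, gets one such check, which is the first reading in the qualifying state. After that nothing changes, so no further check is required. The second reading depends on investigator discretion (Section 3.1) or on clinical indication (Appendix 2).

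**Step 4. Can the state arise?** Yes, by down-titration. The baseline row can also create it: calcium above 9.5 mg/dL, less than 500 mg oral calcium and no calcitriol means a start at 25 µg without supplements. Inclusion criterion 7 requires calcium at or below ULN, so such a subject enters less than 10.2 − 9.5 = 0.7 mg/dL below it (0.5 at an assumed ULN of 10.0, 1.0 at 10.5). This shows that the case is foreseeable. It does not show how often it occurs.

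**The case against.** The strongest reply is that precedence is largely settled. Section 3.1 uses binding language and Appendix 2 describes itself as non-mandatory guidance for adjusting supplements, which this subject does not take. Where Appendix 2 means to bind, it says so in capitals. This stands: Section 3.1 should govern. It does not remove the problem, because the same appendix does state one mandatory rhPTH[1-84] stop, and a reader may take that as the complete list. No sentence says which text prevails.

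Several other replies also stand.

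- The stop requires persistence, so the texts agree at a first high reading.
- The protocol leaves other routes open: draws at the investigator's discretion, withdrawal for an adverse event or in the subject's interest (Section 4.4), and the medical monitor.
- The SAP pointer carries little weight, since sites do not titrate from a SAP.
- Amendment 6 is dated October 2016, and the re-consent step in Table 6-3 sits in the Months 38/50/62 column. Enrolment had probably closed, so the baseline row would place few or no new subjects in this state.
- A required repeat goes beyond harmonising the texts. Section 3.1 implies that draw but does not order it, so it must be presented as an added procedure.

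A reader might infer that Appendix 2 tells sites to keep dosing every such subject between ULN and 11.9 mg/dL against a mandatory stop. The documents do not support that. Section 3.1 requires no stop on one reading, and Appendix 2 does not claim to override the protocol body.

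**Conclusion.** The inconsistency is real but narrow. Section 3.1's ULN stop is missing from Appendix 2, whose rows say 'Maintain' even at the second qualifying reading. The conflict is confined to subjects at the lowest dose, off all supplements, with two predose values above ULN but not above 11.9 mg/dL taken no more than 5 days apart. Their number is not given and is probably small. The more practical weakness is that neither text orders the repeat draw, and routine visits are too far apart to supply it, so the rule may seldom be tested.

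The 1.7 mg/dL width (1.4 to 1.9 for an assumed ULN of 10.5 to 10.0) might be taken as the size of the risk. It only marks where a conflict is possible if every other condition is met. Appendix 2's omission of the optional reduction above 10.0 mg/dL is not a contradiction, because that rule is permissive.

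Severity is minor: an inconsistency in a safety instruction, with no effect on endpoints or analysis. The conclusion assumes that 25 µg is the lowest regimen and that ULN is near the protocol's general figure.

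**What to change.** 1. In the 9.1-10.5 and 10.6-11.9 mg/dL rows of both post-baseline sets in Appendix 2 (four rows), add:

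> If at the lowest rhPTH[1-84] dose and off all oral calcium and calcitriol, and predose calcium is above ULN, repeat within 5 days; if still above ULN, stop rhPTH[1-84] and consult the medical monitor (Section 3.1).

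2. Add the same repeat instruction to Section 3.1, so that it binds and does not rest on a non-mandatory guideline.
3. List the ULN stop beside the 11.9 mg/dL stop in the synopsis.
4. State in Appendix 2 that Section 3.1 prevails where the two differ.

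The cost is a few sentences of amendment text and one explicit extra local calcium draw in the few subjects who are at the lowest dose, off supplements and above ULN. Section 3.1's rule cannot operate without that draw. No statistical analysis needs to change.

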**Figure 3-1 Study Design – First 12 Months of Study**

**Figure 3-2 Study Design – Long-term Extension**

\*Subjects who terminate or complete the study and opt to continue treatment on commercial drug (Natpara), will not require follow-up serum calcium and/or phosphate checks, but should continue treatment under the supervision of a physician under approved labeling instructions.  
\*\* Approximately 4 weeks (30 days) following the End of Treatment visit, all subjects will be contacted by telephone in order to assess AEs/SAEs.

### 3.2 Study Duration

The duration of the study was originally intended to be about 1 year. The study has been extended to up to 80 months of treatment with a 4-week follow up call/visit. Therefore, the overall duration of the study is expected to be approximately 81 months.

Study visits will be conducted every 2 months and will continue until the subject voluntarily withdraws or until termination of the study. See Section 6.2 for additional follow-up for subjects who develop antibodies specific to PTH. See Table 6-4 for additional follow-up for subjects who develop antibodies specific to PTH.

## 4 SUBJECT SELECTION AND PARTICIPATION

### 4.1 Number of Subjects

Approximately 50 subjects will be enrolled.

### 4.2 Inclusion Criteria

Subjects who meet all the following inclusion criteria can be enrolled into this study:

1. Signed and dated informed consent form (ICF) before any study-related procedures are performed
2. Previously completed the NPSP558 RELAY study 8 weeks of active therapy and/or previously completed the NPSP558 REPLACE study (Visit 18)
3. Able to perform daily SC self-injections of study medication (or have designee perform injection) via a multidose pen injector into the thigh
4. Willingness and ability to understand and comply with the protocol
5. Women who are: (1) postmenopausal defined as 12 months amenorrhea with appropriate serum follicle stimulating hormone (FSH) levels ( $> 40$  IU/L); (2) surgically sterilized; OR (3) of childbearing potential with a negative pregnancy test at screening and who consent to use two acceptable methods of contraception for the duration of the study, with pregnancy testing at every scheduled visit. Male subjects who have female partners of childbearing potential together also must use 2 acceptable forms of contraception during the subject's participation in the study.
6. Serum creatinine  $< 1.5$  mg/dL at enrollment
7. Total serum calcium  $\leq$  ULN based on local laboratory result prior to enrollment

8. Serum 25(OH) vitamin D  $\leq$  1.5 times the ULN within approximately 16 weeks prior to enrollment

#### **4.3 Exclusion Criteria**

Subjects who meet any of the following exclusion criteria at baseline (Visit 1) are not eligible for enrollment in this study:

1. Any condition that, in the investigator's opinion after consultation with the sponsor, would preclude the safe use of PTH
2. Any disease or condition, in the opinion of the investigator, which has a high probability of precluding the subject from completing the study or where the subject cannot or will not appropriately comply with study requirements
3. Pregnant or lactating woman

